7.5.1. Analysis Addressing the Primary Study Objective (Safety)

Solicited symptoms occurring during the 28 days following vaccination will be summarized by treatment group and by relatedness. The incidence and severity of solicited AEs to the vaccine over the 28-day follow-up period will be calculated. Presentations will include the number and percentage of subjects with at least 1 local AE, and at least 1 general (systemic) AE, as well as the incidence of each AE individually.

The number of subjects with at least 1 incidence of an unsolicited AE reported up to 28 days after vaccination will also be summarized overall and by treatment group. The severity and temporal relationship of the unsolicited AEs to vaccination will also be assessed. Presentations will also summarize unsolicited AEs by grade and vaccine-relatedness. Serious AEs occurring at any point during the trial will be summarized and relatedness to vaccine will be assessed. The incidence rate of solicited AEs may be compared between each treatment group and placebo using Fisher's exact test and logistic regression.

The level of vaccinemia (on days 1 [at 0 and 6 hours], 2, 4, 8, 15, and 29) and shedding will be assessed on all subjects. The proportion of subjects with detected vaccinemia, as well as the geometric mean and AUC of vaccinemia level, will be presented at each time point where data are collected. The relationship between vaccinemia level and dose will be explored in a mixed model for repeated measures (MMRM) analysis that incorporates dose level, time, and other potential predictive factors. A similar model will be used to explore the relationship between dose and the AUC of the vaccinemia level.

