7.5.2. Analysis Addressing the Immunologic Study Objective

Primary analysis of immunogenicity will be based on the PP analysis population; a secondary analysis of immunogenicity may be based on the mITT population. All immunogenicity analyses will be performed by vaccine treatment group. If a subject withdraws from the study, only the data collected to the point of withdrawal will be included. Immunogenicity will be described in terms of the number of responders and the magnitude of response over time.

For the continuous immunogenicity endpoints such as IgG ELISA antibody titers (on days 1, 15, 29, 85, and 181) and neutralizing antibody titers PsVNT (on days 1, 15, 29, 85, and 181). The 95% confidence limits will be obtained by first obtaining the 95% confidence limits for the mean of log₁₀ translated values and then exponentiating the confidence limits.

Mean fold increase in PHV01 IgG ELISA titers and PsVNT on days 8, 15, 29, 85, and 181 compared to baseline (day 1) will be provided. For each respective study day, \log_{10} translated values from baseline will be subtracted from the respective study day for each subject and averaged within vaccine treatment group and dose level. The result will be exponentiated to return to the original scale. The analysis of mean fold increase in PHV01 IgG ELISA titers and PsVNT over time will be performed using MMRM.

Distribution of PHV01 IgG ELISA titers and PsVNT on days 8, 15, 29, 85, and 181 will be displayed as reverse cumulative distribution curves. Median duration of vaccinemia determined by RT-qPCR will be provided. The duration will be presented graphically using the Kaplan-Meier method. Proportion of subjects with vaccinemia detected by RT-qPCR, by study day through days 1 (at 0 and 6 hours), 2, 4, 8, 15, and 29 and by vaccine treatment group, will be provided with 95% CIs.

Seroconversion rate determined on days 8, 15, 29, 85, and 181 and corresponding 95% CI will be provided. Logistic regression models may be performed for comparison between dose levels and placebo.

Additional immunogenicity dose response between dose groups and over time for continuous and categorical endpoints may be assessed using MMRM and logistic regression models, respectively. For continuous endpoints, log_{10} translated values will be entered in the model as the dependent variable(s). Regarding dose-response analyses more details will be provided in the SAP.

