- Incidence of AESIs up to Day 181, including pneumonitis, acute respiratory distress syndrome, multiorgan failure, a hemorrhagic diathesis, certain neurologic events (encephalitis, myelitis, aseptic meningitis, optic neuritis, transverse myelitis, generalized convulsions, Guillain-Barré Syndrome, acute disseminated encephalomyelitis), thrombocytopenia, anaphylaxis, and vasculitides.

Secondary safety endpoints include the following:

• PHV01 in blood on Days 1 (at 0 and 6 hours), 2, 4, 8, 15, and 29, as detected by quantitative reverse transcription polymerase chain reaction (RT-qPCR)

- o Proportion of subjects with viremia detected by RT-qPCR
- Median duration of viremia, determined by RT-qPCR
- o Geometric mean level of viremia, geometric mean peak level of viremia, and area under the curve (AUC)
- PHV01 in urine, saliva, biopsy, joint fluid, vesicle fluid, or swab of other suspect lesions on Days 1 (at 0 and 6 hours), 2, 4, 8, 15, and 29, as detected by RT-qPCR
 - o Proportion of subjects with PHV01 detected by RT-qPCR
 - o Median duration of PHV01, determined by RT-qPCR
 - Geometric mean copy number of PHV01, geometric mean peak copy of PHV01, and AUC

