4.4.3. Vaccine Viremia

The level of vaccine viremia and shedding will be assessed for all subjects by RT-qPCR in blood, urine, and saliva. For RT-qPCR results reported as < LLOQ, the result will be assigned a value of LLOQ/2 at such visit for computations. For RT-qPCR results reported as < LOD, the result will be assigned a value of 1 genome copies/mL for computations.

Vaccine viremia duration is defined as the time from first administration of study vaccine to vaccine viremia clearance detected by RT-qPCR. Subjects without vaccine viremia clearance will be censored at the last evaluable assessment.

The distribution for vaccine viremia duration by treatment group will be estimated by Kaplan-Meier methodology and the 25th percentile, median, 75th percentile, number and percentage of events and censored observations, and appropriate 95% CIs will be presented. If the 95% CIs of

three PHV01 groups overlap then the analysis will be repeated comparing the combined PHV01 group with the placebo group. The corresponding Kaplan-Meier curves will also be generated.

The proportion of subjects with vaccine viremia in blood, urine, and saliva, as well as the geometric mean of vaccine viremia level and the geometric mean of peak level, will be presented on Day 1 (at 0 and 6 hours), 2, 4, 8, 15, and 29 by specimen type, dose level and the combined PHV01 group.

Reverse cumulative distribution curves of rVSV RNA copies by specimen type will be generated by treatment group on Day 1 (at 0 and 6 hours), 2, 4, 8, 15, and 29, respectively, where the x-axis will be the observed log-10 transformed titers and the y-axis will be the percentage of subjects having a log-10 transformed titer greater than or equal to each of the observed log-10 transformed titers on the x-axis.

Line plots will present number of rVSV RNA copies by specimen type at each visit by treatment group.

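### The SAP omits, without saying so, the protocol's 95% CIs on the proportion vaccinemic and its dose models for vaccinemia level and AUC; neither document's analysis section gives an ever-positive proportion

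*SAP*

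**What the plan says.** **Protocol.** Section 7.5.2 plans the "Proportion of subjects with vaccinemia detected by RT-qPCR, by study day through days 1 (at 0 and 6 hours" and on the later sampling days, "and by vaccine treatment group, will be provided with 95% CIs". Section 7.5.1 says: "The relationship between vaccinemia level and dose will be explored in a mixed model for repeated measures (MMRM) analysis that incorporates dose level, time". It leaves further predictors open, then adds: "A similar model will be used to explore the relationship between dose and the AUC of the vaccinemia level". These sentences say *will*, while the same sections use *may* for optional analyses.

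**SAP.** Section 4.4.3 presents "The proportion of subjects with vaccine viremia in blood, urine, and saliva, as well as the geometric mean of vaccine viremia level" and of its peak, at each sampling time, by specimen type, dose level and combined PHV01 group. The only intervals it names are those for Kaplan-Meier duration. Section 4.4.4 summarises AUC to Day 8 and to Day 29 descriptively by group. Section 3.2 confines formal testing to the immunogenicity endpoints and promises CIs only where a later section describes them. MMRM appears in the abbreviation list and nowhere in the body.

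**Declaration of changes.** SAP 1.1.1 says the document will outline differences from the protocol. Section 6 says only that changes will be summarised in the study report. Section 8.1 records edits to 4.4.3, but only for handling results below LOD and LLOQ.

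**Endpoint.** Both documents list, among the secondary safety endpoints, the "Proportion of subjects with viremia detected by RT-qPCR".

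**The concern.** Viremia and shedding make up the whole secondary objective, and Protocol 1.3 treats vaccinemia as the evidence that the vaccine replicates in vivo. With 10 subjects per dose and 6 on placebo, a percentage without an interval invites over-reading, above all when it is 0% or 100%. Without a dose estimate, the report can show vaccinemia by dose but cannot say how large any dose effect is or how well it is estimated. Because the omission is undeclared, a reader of the report could not tell whether the planned analyses were withdrawn on purpose or overlooked. The endpoint is also worded per subject, yet no analysis counts each subject once across visits.

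**Working it through.** **1. Commitments set against the plan**

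| Item | Protocol | SAP |
|---|---|---|
| Proportion vaccinemic by day and group | With 95% CIs (7.5.2) | Given, no CI (4.4.3) |
| Vaccinemia level and dose | MMRM with dose level and time (7.5.1) | Geometric means and peaks by dose (4.4.3) |
| AUC and dose | Similar model (7.5.1) | Descriptive by group (4.4.4) |
| Duration | Median, Kaplan-Meier plot (7.5.2) | Kaplan-Meier with 95% CIs (4.4.3) |
| Proportion ever positive | Not analysed | Not analysed |

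Rows 1 to 3 are the omissions. Row 4 is kept and strengthened. Row 5 is a gap in both documents.

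**2. The plan's own precision figures**

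For zero events in n subjects, the upper two-sided 95% Clopper-Pearson limit is 1 − 0.025^(1/n).

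- n = 10: 1 − 0.025^(1/10) = 30.85% (30.9% in Protocol 7.1 and SAP 3.1)
- n = 30: 1 − 0.025^(1/30) = 11.57% (11.6% in SAP 3.1)

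Both figures reproduce. The documents use them for adverse events.

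**3. The same calculation for detection of virus**

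Group sizes are 10 per dose, 30 vaccinees in all, and 6 placebo. The documents give no expected viremia rates, so the counts below are illustrative.

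| Detected | Exact 95% CI |
|---|---|
| 0/10 | 0 to 30.8% |
| 5/10 | 18.7% to 81.3% |
| 10/10 | 69.2% to 100% |
| 0/30 | 0 to 11.6% |
| 15/30 | 31.3% to 68.7% |
| 0/6 (placebo) | 0 to 45.9% |

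At 5/10 the interval is 81.3 − 18.7 = 62.6 points wide.

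**4. Why per-visit rates do not give the ever-positive proportion**

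Assume detection rates of 10, 40, 30, 10, 0 and 0% at the six post-dose samples (6 hours, Days 2, 4, 8, 15 and 29).

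- Lower bound, if the same subjects are positive repeatedly: the largest rate, 40%.
- Upper bound, if every positive sample comes from a different subject: 10 + 40 + 30 + 10 = 90%.
- If visits were independent: 1 − 0.9 × 0.6 × 0.7 × 0.9 = 66%.

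One set of visit rates is thus compatible with anything from 4 to 9 of 10 subjects ever positive.

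**5. The AUC formula**

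As printed in SAP 4.4.4, each term is half the *difference* of adjacent log10 RNA values, times the time step. The trapezoid rule, which that section names, uses half their *sum*. For two adjacent values of 3 log10 taken 2 days apart (an illustration), the printed term is ½ × (3 − 3) × 2 = 0, while the trapezoid area is ½ × (3 + 3) × 2 = 6. A dose model for AUC needs this corrected first. If the signed copy shows a plus sign, nothing needs changing.

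**The case against.** The strongest reply is that little is lost. An exact interval follows from the count and the group size, so any reader can compute it. SAP 4.4.5 tabulates PCR results by visit and treatment group, placebo included, and lists all laboratory data. The protocol says only that the dose relationship will be explored. This stands as far as it goes: the data remain recoverable. But it covers the intervals only. Nothing in the SAP tables yields the modelled dose effect, and nothing tells the reader that it was planned.

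Five stronger readings are tempting, and the documents do not support them.

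- *The secondary objective yields only percentages.* It does not. Duration has Kaplan-Meier quartiles with 95% CIs. Levels, peaks, AUC and reverse cumulative curves are shown by group. AUC is correlated with titers and symptom index.
- *The SAP dropped the ever-positive proportion.* Protocol 7.5.1 and 7.5.2 also present detection by time point. The gap is against the endpoint's wording and is common to both documents.
- *A misleading 0% for saliva follows from the omission.* The protocol's CI and model commitments are worded for vaccinemia. None was made for urine or saliva.
- *The Day 29 dose choice needs a viremia dose estimate.* SAP 3.12 includes RT-qPCR results in the interim analysis, but Protocol 7.2 says they may be added when available. No section makes dose selection depend on a modelled viremia effect.
- *Thirty vaccinees are known to be enough for a dose slope.* The documents give no between-subject SD for viremia. SAP 4.4.3 scores results below LOD as 1 copy, so log10 = 0. If half the subjects were non-detects and half were near 3 log10 (assumed), the SD would be about 1.5. No power claim is made here.

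**Conclusion.** The point holds as a protocol–SAP discrepancy. Two committed analyses of blood vaccinemia are absent and the absence is undeclared: the 95% CIs on the proportion vaccinemic by day and group, and the dose models for level and AUC. Apart from Kaplan-Meier duration, viremia results are descriptive by dose, with no interval and no dose-effect estimate. The missing intervals are wide: the upper limit is 30.8% at 0/10, 11.6% at 0/30 and 45.9% at 0/6. These limits rest only on the planned group sizes and the exact method. The missing ever-positive proportion is a separate, smaller gap in both documents; the 40% to 90% range illustrating it rests on assumed visit rates. This should be put right, but it does not invalidate the trial or its data.

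**What to change.** 1. **Proportion vaccinemic, SAP 4.4.3.** Add Clopper-Pearson 95% CIs to the per-day proportion in blood, by dose, combined PHV01 and placebo. SAP 4.3.2 already uses this method for seroconversion.
2. **Improvement beyond the protocol.** Add a row for subjects ever positive, meaning any post-dose sample. State the positivity rule; Protocol 3.1.3 defines vaccinemia in blood as a result at or above LLOQ. Give the same intervals for urine and saliva.
3. **Dose models, SAP 4.4.3 and 4.4.4.** Correct the AUC formula, then restore the models of Protocol 7.5.1 for vaccinemia level and AUC. Report the dose effect with a 95% CI, and specify the model terms, visits and covariance structure in advance. AUC has one value per subject in each window, so its model needs no repeated-measures term.
4. **If the models are dropped on purpose,** record that and the reason in SAP Section 6.

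The cost is SAP wording, a few table columns and the model programming. No new data are needed.

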4.4.4. Vaccine Viremia Area Under the Curve

Vaccine viremia area under the curve (AUC) will be estimated using the trapezoid rule. Calculations will be performed relative to the first vaccination for each subject.

Calculations relative to the first vaccination will be based on figures displaying the number of copies of rVSV RNA on the Y axis and the actual number of days after the first vaccination that the blood sample was taken on the X axis. The general formula used to calculate AUC will be:

$$AUC_{i} = \sum_{i=0}^{n[\]} \frac{1}{2} \times [(RNA\ Copies_{k} - RNA\ Copies_{k-1})] \times [Days_{k} - Days_{k-1}]$$

Where the index i represents subject, index k represents the time points measured in actual days in which the viremia sample was drawn, 'RNA Copies' represents the base-10 log transformed number of rVSV RNA copies, and Days represents the actual days the blood sample for viremia was taken.

Two sets of AUC calculations will be performed: AUC from first vaccination to Day 8, and AUC from first vaccination to Day 29. These quantities summarize viremia after the first vaccination.

AUC from first vaccination to Day 8 will be calculated using the above formula where k = Days 1 (at 0 and 6 hours), 2, 4, and 8.

AUC from first vaccination to Day 29 will be calculated using the above formula where k = Days 1 (at 0 and 6 hours), 2, 4, 8, 15, 29.

Each set of AUC calculations will be summarized descriptively by the geometric mean AUC, geometric standard deviation, median, minimum, and maximum value, by treatment group. Descriptive statistics will also be presented for the combined PHV01 treatment group. Calculation of the geometric mean AUC and standard deviation will follow the approach outlined in Section 4.4.3.

Spearman's rank correlation will be used to estimate the association between viremia AUC and IgG ELISA antibody titers for each PHV01 vaccine dose group including the combined PHV01 group at Day 29. A similar analysis will be performed to estimate the correlation between viremia AUC and PsVNA titers.

Spearman's rank correlation will be used to estimate the association between the viremia AUC (Day 0 to 29) with the AE symptom index calculated for solicited local AEs that occurred from Day 0 to Day 29 for each vaccine dose group. The same analysis will be repeated using the AE symptom index calculated for systemic AEs.

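### The viremia AUC formula in SAP 4.4.4 is not the trapezoid rule that the text names, and the planned geometric mean of AUC is undefined for any subject whose samples are all below LOD

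*SAP*

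**What the plan says.** SAP 4.4.4 states the method in words: "Vaccine viremia area under the curve (AUC) will be estimated using the trapezoid rule". It then prints a general formula whose height term is "RNA\ Copies_{k} - RNA\ Copies_{k-1", multiplied by one half and by the time between samples. The summation index is i, which the same section defines as the subject; the time point is k. Both AUC windows are to be computed with this formula: one with "k = Days 1 (at 0 and 6 hours), 2, 4, and 8", the other with "k = Days 1 (at 0 and 6 hours), 2, 4, 8, 15, 29".

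On scale, the section describes a plot with copy numbers on the vertical axis, but defines the formula's term differently: "RNA Copies' represents the base-10 log transformed number of rVSV RNA copies".

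On summary: "Each set of AUC calculations will be summarized descriptively by the geometric mean AUC", together with the geometric SD, median, minimum and maximum, by treatment group. For the geometric calculations it refers back to SAP 4.4.3. That section handles single PCR results only: "For RT-qPCR results reported as < LLOQ, the result will be assigned a value of LLOQ/2 at such visit for computations", and "For RT-qPCR results reported as < LOD, the result will be assigned a value of 1 genome copies/mL for computations". It has no rule for an AUC of zero or below.

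AUC is a secondary safety endpoint (Protocol 3.1.2, SAP 1.2.5.1). SAP 4.4.4 also correlates it, by Spearman's method, with Day 29 IgG ELISA titers, PsVNA titers, and the local and systemic symptom indices.

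**The concern.** There are two separate defects.

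1. **The formula contradicts the named method.** A trapezoid has area one half times the sum of its two heights times its width. With a difference in place of the sum, the result is not an area. A programmer who follows the equation gets a different quantity from one who follows the sentence above it, and that quantity can run opposite to viremia. A correlation with antibody or symptoms could then be reported with the wrong sign.

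2. **The summary does not fit the scale.** One copy/mL is 0 on the log10 scale. A subject with no detectable RNA at any visit has AUC 0 even under the correct rule, and the logarithm of 0 does not exist. The SAP asks for the geometric mean in every treatment group, including placebo, where such subjects are to be expected. This does not depend on the sign in the formula.

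**Working it through.** The documents give no numerical AUC, so there is no figure to reproduce. The check applies both formulas to the SAP's time grid.

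**Inputs.** Days since dosing t = 0, 0.25, 1, 3, 7, 14, 28 (SAP 4.4.4, with the 6-hour sample set to 0.25 days in SAP 3.2); y = log10 copies; below LOD, y = 0. The profiles are assumed for illustration.

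**Formulas.**
- Printed: sum of 0.5 × (y_k − y_{k−1}) × (t_k − t_{k−1})
- Trapezoid: sum of 0.5 × (y_k + y_{k−1}) × (t_k − t_{k−1})

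**One profile in full** (A: 0, 2, 4, 3, 0, 0, 0):
- Trapezoid: 0.25 + 2.25 + 7 + 6 = 15.5
- Printed: 0.25 + 0.75 − 1 − 6 = −6.0

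**More profiles** (trapezoid / printed):

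| Profile | To Day 8 | To Day 29 |
|---|---|---|
| 0, 0, 2, 1, 0, 0, 0 | 5.75 / −2.25 | 5.75 / −2.25 |
| 0, 1, 3, 2, 0, 0, 0 | 10.625 / −4.125 | 10.625 / −4.125 |
| A: 0, 2, 4, 3, 0, 0, 0 | 15.5 / −6.0 | 15.5 / −6.0 |
| 0, 2, 4, 3, 1.5, 0, 0 | 18.5 / −3.0 | 23.75 / −8.25 |
| B: 0, 2, 4, 3, 2, 0, 0 | 19.5 / −2.0 | 26.5 / −9.0 |
| 0, 2, 5, 4, 2, 0, 0 | 23.875 / −3.625 | 30.875 / −10.625 |
| constant 3 | 21 / 0 | 84 / 0 |
| all below LOD | 0 / 0 | 0 / 0 |

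To Day 29, the first six profiles come out in exactly reversed order. To Day 8 they do not: A and B keep their order.

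**Why.** In the printed formula an interior visit has weight 0.5 × [(t_k − t_{k−1}) − (t_{k+1} − t_k)], which is negative whenever the intervals lengthen. The nominal intervals are 0.25, 0.75, 2, 4, 7 and 14 days, so the weights are:
- To Day 29, printed: −0.125, −0.25, −0.625, −1, −1.5, −3.5, +7
- To Day 29, trapezoid: 0.125, 0.5, 1.375, 3, 5.5, 10.5, 7
- To Day 8, printed: −0.125, −0.25, −0.625, −1, +2

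Only the last visit counts positively. If y = 0 on Day 29 and viremia occurred earlier, the printed Day 29 AUC must be negative. In the Day 8 window, RNA still present on Day 8 pulls the value up, so the distortion is not a simple reversal. SAP 4.4.4 uses actual days, and visit windows can change a weight: with the Day 4 visit on Day 5 and the Day 8 visit on Day 7, the Day 4 weight is 0.5 × [(4 − 1) − (6 − 4)] = +0.5. The sign statement is therefore for nominal times.

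**Illustrative simulation** (30 vaccinees, 500 runs; Day 2 peak with mean 3 and SD 0.8 log10; decline 0.3 to 1.0 log10 per day; LOD = LLOQ/2.5; all assumed). The documents give no LLOQ, so three values were tried.

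| Assumed LLOQ | Spearman, printed vs trapezoid: Day 8 | Day 29 | Trapezoid AUC to Day 29 equal to 0 |
|---|---|---|---|
| 10 | −0.67 | −1.00 | 0.1% |
| 100 | −0.92 | −1.00 | 4.5% |
| 1000 | −1.00 | −1.00 | 31.3% |

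The Day 29 result largely follows from the weights once viremia is assumed to clear, so it is not independent evidence.

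**Geometric mean.** With all samples below LOD, every y is log10(1) = 0 and AUC = 0 under either formula; log(0) is undefined. On the copies scale the same subject has AUC 1 × 7 = 7 to Day 8 and 1 × 28 = 28 to Day 29, and the geometric mean exists.

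**The case against.** The strongest reply is that the prose is right. The sentence names the trapezoid rule, a programmer who follows it avoids the error, and negative areas would stand out in the planned median, minimum and maximum. In the text version of the SAP the equation's upper limit is visibly damaged, so the minus sign and index may be damaged too. This stands as a reason to check the original page and to treat the reversal as conditional on literal coding. It does not remove the instruction to use the printed formula, and it does not touch the geometric mean problem.

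A reader might infer more than the documents support:

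- *Every correlation changes sign.* Only the symptom-index correlations are tied to the Day 29 window. The SAP does not say which AUC enters the IgG and PsVNA correlations, and Day 8 order can be kept. Viremia lasting to the final visit also escapes the pattern.
- *Every non-viremic subject, and every placebo recipient, has AUC 0.* Protocol 3.1.3 defines vaccinemia as a result at or above LLOQ. A detected result below LLOQ is non-viremic but is set to LLOQ/2, giving a positive contribution if LLOQ exceeds 2 copies/mL. Only subjects with all samples below LOD have AUC 0.
- *Zeros will be dropped silently, inflating exposure most at the lowest dose.* Software may instead return zero, an error or a missing value, and the documents give no rate of undetected RNA by dose.
- *Escalation is at risk.* Pausing, halting and escalation rest on AEs and Day 8 safety data (Protocol 3.7.2, SAP 1.2.3). Viremia level, peak, duration and proportion do not use this formula.

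**Conclusion.** The point holds on both counts, within limits.

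- **Formula.** As it reads, it is not the trapezoid rule. Applied literally at nominal times, it makes the Day 29 AUC negative for any subject with earlier viremia and y = 0 on Day 29, and reverses or nearly reverses ranks in correlations using that AUC. For the Day 8 AUC the values are wrong and the reversal may be only partial. This rests on the minus sign being in the original and on the formula, not the prose, being coded.
- **Geometric summary.** It is undefined in any group containing a subject with all samples below LOD, whichever sign is printed. This rests only on the log10 definition and the 1 copy/mL substitution. It is expected in placebo and possible among vaccinees.

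The affected outputs are a secondary safety endpoint, summarised descriptively, and its correlations. The median, minimum and maximum are unaffected by the geometric mean problem. The rule needs correcting before the analysis is programmed, but it does not bear on subject safety or dose escalation.

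**What to change.** 1. Check the equation on the original page, then print AUC_i = sum over k = 1..n of 0.5 × (y_ik + y_i,k−1) × (t_ik − t_i,k−1), with k = 0 the pre-dose sample.
2. Settle the conflict between the copy-number axis and the log10 term by one of two routes, both valid:
   - (a) keep log10 values and summarise AUC by arithmetic mean, SD, median and range, with zeros included; or
   - (b) compute AUC on the copies scale, where the 1 copy/mL floor keeps it positive, and keep the geometric mean and geometric SD.
3. State which AUC window enters the IgG and PsVNA correlations.

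The cost is one formula, one or two sentences in the SAP and minor programming. The protocol endpoint is unchanged, since Protocol 3.1.2 lists AUC without requiring its geometric mean.
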